4.1.2 Exclusion Criteria

Patients who meet any of the following criteria will be excluded from study entry:

- Pregnant or lactating, or intending to become pregnant during the study
 - Women who are not postmenopausal (postmenopausal defined as ≥ 12 months of non-therapy-induced amenorrhea) or surgically sterile must have a negative pregnancy test result within 2 days prior to initiation of study drug.
- Hypersensitivity to monoclonal antibodies or to any *constituents* (*sodium succinate, sucrose, polysorbate 20*) of MHAA4549A study drug
- Hypersensitivity to the active substance or to any excipients of oseltamivir
- Investigational therapy within the 30 days prior to study treatment
- Received prior therapy with any anti-influenza monoclonal antibody therapy (including MHAA4549A) *within* 8 months prior to study treatment
- Current treatment (within 7 days of dosing) with probenecid, amantadine, or rimantidine

- Patients who have taken more than a total of 6 doses (3 doses of peramivir) of anti-influenza therapy (e.g., oseltamivir, zanamivir, *laninamivir*, peramivir) in the period from onset of symptoms and prior to study treatment
- Admission >48 hours prior to study treatment
- Onset of influenza symptoms (including fever, chills, malaise, dry cough, loss of appetite, myalgias, coryza, or nausea) >5 days prior to study treatment
- Positive influenza B or influenza A+B infection within 2 weeks prior to study treatment
- High probability of mortality in the next 48 hours as determined by the investigator
- Patient requiring home or baseline oxygenation therapy
- Patient with history of chronic lung disease *with a documented* SpO₂ < 95% *off oxygen*
- Patient on a chronic dose of corticosteroids exceeding 10 mg/day of prednisone or equivalent steroid dose for a duration of greater than 14 days within 30 days of entry into study
- Creatinine clearance ≤ 10 mL/min
- Patients who received nasally administered influenza A vaccine within 7 days *prior to screening*
- Patients with the following significant immune suppression:
 - Bone marrow or solid organ transplant in the previous 12 months
 - Cancer chemotherapy in the previous 12 months
 - HIV infection with most recent CD4 < 200 cells/mL
 - Other significant immune suppression as determined by the investigator in discussion with the Sponsor Medical Monitor
- Patient on ECMO at time of randomization
- Any disease or condition that would, in the opinion of the site investigator or Sponsor, place the subject at an unacceptable risk of injury or render the subject unable to meet the requirements of the protocol

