Appendix 9 DAIDS Toxicity Grading Tables for Laboratory Abnormalities

Adapted from Division of Microbiology and Infectious Diseases (DMID) Adult Toxicity Table November 2007 DRAFT and FDA Guidance document 'Toxicity Grading Scale from Healthy Adult and Adolescent Volunteers Enrolled in Preventative Vaccine Clinical Trials

Abbreviations used in the table:

■; CPK=creatin phosphokinase; Dec=Decreased; IV=Intravenous; LLN=Lower limit of normal; Mod=Moderate; Req=Required; Rx=Therapy; SGOT=serum glutamic oxaloacetic transaminase; SGPT=serum glutamic pyruvic transaminase; ULN=Upper limit of normal.

HEMATOLOGY				
	Grade 1	Grade 2	Grade 3	Grade 4
Hemoglobin	9.5 – 10.5 g/dL	8.0 – 9.4 g/dL	6.5 – 7.9 g/dL	<6.5 gm/dL
Absolute Neutrophil Count	1,000 – 1,500/mm ³	750 – 999/mm ³	500 – 749/mm ³	<500/mm ³
*Platelets	125,000 – 140,000/mm ³	100,000 – 124,999/mm ³	25,000 – 99,999/mm ³	<25,000/mm ³
WBCs	11,000 – 13,000/mm ³	13,000 – 15,000/mm ³	15,000 – 30,000/mm ³	>30,000 or <1,000/mm ³
*Lymphocytes Decrease – cell/mm ³	750 – 1,000	500 – 749	250 – 499	<250
*Eosinophils – cell/mm ³	650 – 1500	1501 – 5000	>5000	Hyper eosinophilic
Abnormal Fibrinogen	Low: 100 – 200 mg/dL High: 400 – 600 mg/dL	Low: <100 mg/dL High: >600 mg/dL	Low: <50 mg/dL	Fibrinogen associated with gross bleeding or with disseminated coagulation
Fibrin Split Product	20 – 40 mcg/mL	41 – 50 mcg/mL	51 – 60 mcg/mL	>60 mcg/mL
Prothrombin Time (PT)	1.01 – 1.25 x ULN	1.26 – 1.50 x ULN	1.51 – 3.0 x ULN	>3 x ULN
Activated Partial Thromboplastin Time (APTT)	1.01 – 1.66 x ULN	1.67 – 2.33 x ULN	2.34 – 3 x ULN	>3 x ULN
Methemoglobin	5.0 – 9.9%	10.0 – 14.9%	15.0 – 19.9%	>20.0%

From the FDA Guidance document 'Toxicity Grading Scale from Healthy Adult and Adolescent Volunteers Enrolled in Preventative Vaccine Clinical Trials'

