- Patient with history of chronic lung disease *with a documented* $\text{SpO}_2 < 95\%$ *off oxygen*
- Patient on chronic dose of corticosteroids exceeding 10 mg/day of prednisone or equivalent steroid dose for a duration of greater than 14 days within 30 days of entry into study
- Creatinine clearance ≤ 10 mL/min
- Patients who received nasally administered influenza A vaccine within 7 days *prior to screening*

- Patients with the following significant immune suppression:
 - Bone marrow or solid organ transplant in the previous 12 months
 - Cancer chemotherapy in the previous 12 month
 - Human immunodeficiency virus (HIV) infection with most recent CD4 <200 cells/mL
 - Other significant immune suppression as determined by the investigator in discussion with the Sponsor Medical Monitor
- Patient on extracorporeal membrane oxygenation (ECMO) at time of randomization
- Any disease or condition that would, in the opinion of the site investigator or Sponsor, place the subject at an unacceptable risk of injury or render the subject unable to meet the requirements of the protocol

Length of Study

This study will consist of the following study periods:

- A screening period of 48 hours, beginning at time of hospital admission
- A treatment period of 1 day, during which patients will receive a single dose of MHAA4549A or placebo and a minimum of 5 days of oseltamivir.
- A follow-up period beginning at hospital discharge through 60 days post study drug (MHAA4549A/placebo) administration

End of Study

The end of the study is defined as the first day when all patients have had a study completion visit or early termination visit or have otherwise been discontinued from the study.

Outcome Measures

Safety Outcome Measures

The safety outcome measures for this study are as follows:

- AEs and clinical laboratory abnormalities
- Vital signs, physical findings, ATAs, and clinical laboratory results during and following administration of MHAA4549A

Efficacy Outcome Measures

The primary outcome measure for this study is as follows:

- Time to normalization of respiratory function defined as:
 - The time to cessation of O₂ support resulting in a stable SpO₂ ≥ 95%

The secondary efficacy outcome measures for this study are as follows:

- *Clinical status of patient at Days 1-7, 14, and 30. This is an ordinal outcome with six mutually exclusive categories:*
 1. *Death;*
 2. *In the ICU;*
 3. *Non-ICU hospitalization, requiring supplemental oxygen;*

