4.6.1 Informed Consent Forms and Screening Log

Written informed consent for participation in the study must be obtained before performing any *study-related procedures*. Informed consent by authorized representatives may be obtained only if allowed by and in accordance with local regulations and Independent Review Board (IRB)/Independent Ethics Committee (IEC)

policies and procedures. Informed Consent Forms (ICF) for enrolled patients and for patients who are not subsequently enrolled will be maintained at the study site.

All screening evaluations must be completed and reviewed to confirm that patients meet all eligibility criteria before randomization. The investigator will maintain a screening log to record details of all patients screened and to confirm eligibility or record reasons for screening failure, as applicable.

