4.6.10 Laboratory, Biomarker, and Other Biological Samples

Samples for the laboratory tests listed in [Table 3](#) and [Table 4](#) will be sent to the study site's local laboratory for analysis at screening and during the study, respectively.

Table 3 Laboratory Tests at Screening

Hematology:	Clinical Chemistry:
Hemoglobin	Thyroid stimulating hormone (optional)
Hematocrit	
Erythrocyte count (RBC)	Serology:
Leukocytes (WBC)	HIV Serology
Neutrophils (segmented and bands if clinically indicated)	
Lymphocytes	Misc:
Monocytes	Pregnancy Test (urine or serum; women of child-bearing potential)
Eosinophils	
Basophils	
Platelets	

Note: Investigators must document their review of each laboratory report by signing (or initialing) and dating each report.

Table 4 Laboratory Tests during the Study

Hematology:	Clinical Chemistry (Blood):
Hemoglobin	Sodium
Hematocrit	Potassium
Erythrocyte count (RBC)	Bicarbonate
Leukocytes (WBC)	Chloride
Neutrophils (segmented and bands if clinically indicated)	Calcium
Lymphocytes	Phosphorus
Monocytes	Magnesium
Eosinophils	Glucose
Basophils	Urea nitrogen (BUN) or urea
Platelets	Creatinine
	Total cholesterol
	Total protein
Coagulation:	Albumin
Activated partial thromboplastin time (APTT)	Total bilirubin
Prothrombin time (PT)	Alkaline phosphatase
International Normalized Ratio (INR)	Aspartate aminotransferase (AST)
	Alanine aminotransferase (ALT)
Urinalysis:	Amylase
pH	Gamma-glutamyl transpeptidase (GGT) (if clinically indicated)
Specific gravity	
Glucose	C-reactive protein (CRP) (optional)
Protein	Erythrocyte Sedimentation Rate (ESR) (optional)
Ketones	
Blood	
Bilirubin	Misc:
Nitrite	Pregnancy Test (urine or serum ; if clinically indicated)
Leukocyte esterase	
Microscopic examination (if clinically indicated)	

Note: Investigators must document their review of each laboratory report by signing (or initialing) and dating each report.

The following samples will be sent to the Sponsor or a designee for PK or ATA analysis:

- █ [REDACTED]
- Serum samples for ATA testing (see [Appendix 1a](#) and [Appendix 1b](#))
- █ [REDACTED]
- █ [REDACTED]
- █ [REDACTED]
- █ [REDACTED]
- █ [REDACTED]

For sampling procedures, storage conditions, and shipment instructions, see the laboratory manual.

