- ^p Limited, symptom-directed physical examination includes, at a minimum, evaluation of general appearance, dermatological examination of the injection sites, evaluations directed by patient-reported symptoms, and any other evaluations that the investigator deems clinically relevant. Changes from any prior examination should be recorded. New or worsened abnormalities should be recorded as AEs, if appropriate.
- ^q Height will be obtained at screening only. Weight will be obtained at all indicated visits. Height and weight will be recorded in centimeters and kilograms, respectively.
- ^r Local laboratory measurements should be utilized.
- ^s For optional thyroid stimulating hormone test.
- ^t Urinalysis includes pH, specific gravity, glucose, protein, ketones, blood, bilirubin, nitrite, and leukocyte esterase. Microscopic examination (e.g., sediment, RBCs, WBCs, casts, crystals, epithelial cells, bacteria) will be performed if clinically indicated.
- ^u HIV serology result not needed for randomization and a positive result does not require patient discontinuation.

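### The CD4 exclusion is printed per mL, which makes it 1000-fold too low if per mm³ was meant; a lesser point is that the schedule does not secure a creatinine result before randomization

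*Combined protocol and SAP*

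**What the plan says.** **CD4.** Among the immune-suppression exclusions, Section 4.1.2 lists "HIV infection with most recent CD4 < 200 cells/mL". The Version 7 synopsis repeats it: "infection with most recent CD4 <200 cells/mL". No other CD4 figure or unit appears. Tables 3 and 4 (Section 4.6.10) list no CD4 test, so the criterion relies on a value already on record. HIV serology is drawn at screening, but Appendix 1a, footnote u, says "HIV serology result not needed for randomization and a positive result does not require patient discontinuation".

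**Renal function.** Section 4.1.2 also excludes "Creatinine clearance ≤ 10 mL/min". Section 4.6.1 states: "All screening evaluations must be completed and reviewed to confirm that patients meet all eligibility criteria before randomization". Table 3, the screening laboratory list, has one clinical chemistry entry, "Thyroid stimulating hormone (optional"). The screening chemistry mark in Appendix 1a carries footnote s, "For optional thyroid stimulating hormone test". Creatinine is listed in Table 4, and the chemistry panel is first mandatory in the Day 1 column, which is also the randomization column.

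**The concern.** A numeric exclusion works only if the number and its unit pick out the patients it is meant to keep out. A limit of 200 per mL is so far below the scale of the protocol's own lymphocyte grading that the CD4 line, read literally, has almost no effect. There is also a reporting consequence. Section 6.2 promises a summary of eligibility exceptions by treatment group, and under the printed unit an enrolled patient with a very low CD4 count would not be counted as one.

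For creatinine, the question is whether the schedule supplies the evidence that Section 4.6.1 requires. If the result is read only after randomization, a patient can turn out to be ineligible once already allocated. Under Section 6, that patient stays in the efficacy population if the central PCR on the Day 1 sample is positive.

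**Working it through.** **CD4 limit**

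Inputs:
- Printed limit: 200 cells/mL (Section 4.1.2 and synopsis).
- Conversion: 1 mL = 1000 µL = 1000 mm³.
- Internal scale for comparison: the hematology page of Appendix 9, visible in the Version 5 copy, grades "Lymphocytes Decrease – cell/mm ³", with Grade 4 below 250.

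Steps:
1. Printed limit per mm³: 200 / 1000 = 0.2 cells/mm³.
2. A patient with 50 CD4 cells/mm³: 50 × 1000 = 50,000 cells/mL, which is 50,000 / 200 = 250 times the limit. Not excluded.
3. A patient with 1 CD4 cell/mm³: 1 × 1000 = 1000 cells/mL, which is 1000 / 200 = 5 times the limit. Also not excluded. In whole cells per mm³, only a recorded zero would meet the criterion.
4. Limit if per mm³ was meant: 200 × 1000 = 200,000 cells/mL. Ratio to the printed value: 200,000 / 200 = 1000.
5. Grade 4 lymphocyte limit: 250 × 1000 = 250,000 cells/mL, and 250,000 / 200 = 1250. The protocol's most severe lymphopenia grade begins 1250 times above the printed CD4 limit. That grade is for total lymphocytes, so it shows the scale in use and is not a CD4 threshold.

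A text-extraction error is unlikely. The per-mL unit appears in the synopsis and in Section 4.1.2 of both Version 5 and Version 7. The µ symbol survives elsewhere, for example in the platelet row of Appendix 7 and the concentrations in Section 1.2.3. Version 7 also edited this exclusion list and left the unit as it was.

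**Creatinine schedule**

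No arithmetic applies. Set side by side:

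| Place | What it provides |
|---|---|
| 4.1.2 | Creatinine clearance is an exclusion criterion |
| 4.6.1 | All criteria confirmed from screening evaluations before randomization |
| Table 3 and Appendix 1a, footnote s | Screening chemistry is optional TSH only |
| Table 4 and Appendix 1a, Day 1 | Mandatory panel including creatinine |
| 4.6.4 and Appendix 1a notes | Day 1 assessments precede dosing; order relative to randomization not stated |
| 4.6.4 | Standard-of-care results may stand in for screening assessments, but creatinine is not listed as one |

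Other eligibility tests do have a timing rule for the result. The influenza result must be available within the 48-hour screening window (Section 4.6.2), and the pregnancy result within two days before treatment (Appendix 1a, footnote d). Creatinine has none. The rule in Section 4.6.1 and the list meant to support it therefore do not match.

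**The case against.** On CD4, sites may well recognize a misprint and read the limit per µL. The list also has two backstops: a catch-all for other marked immune suppression, judged by the investigator with the Medical Monitor, and a general exclusion for unacceptable risk. The criterion uses a historical value, and the serology result is not awaited, so it screens only patients with known HIV infection and a CD4 count on file. The intended unit is inferred from a table that grades total lymphocytes. All of this stands, and it limits the practical harm. It does not repair the threshold: an objective rule that needs silent correction, or is replaced by case-by-case judgement, is no longer objective.

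On creatinine, the objection is stronger. A reader might infer that creatinine is not measured before randomization, that the renal exclusion cannot operate, or that a breach could surface only after allocation. The documents do not support this. The Day 1 panel is mandatory and precedes dosing, nothing prevents it being drawn and read before randomization, and Section 4.6.1 already obliges the site to know the clearance by then. What remains is an inconsistency between that obligation and the screening list.

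**Conclusion.** The CD4 criterion is wrong as written. The printed limit is 0.2 cells/mm³, an exact conversion. That it is 1000-fold too low rests on one assumption, that cells/mm³ (cells/µL) was intended; the lymphocyte grading scale supports this but does not prove it. Read literally, the criterion excludes essentially nobody. It would go too far to say that severely immunosuppressed patients will therefore enter the trial, since the discretionary exclusions can still keep them out.

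The creatinine point is minor: the schedule does not guarantee a result before randomization, although the eligibility rule needs one. The documents give neither the number of patients affected nor a reason for the renal exclusion, so its size is unknown and no safety rationale can be attributed to it. Neither point is shown to bias the treatment comparison, because eligibility is applied without regard to arm.

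**What to change.** Reconcile and correct the CD4 unit in Section 4.1.2 and in the synopsis. The sponsor should confirm the intended unit, presumably cells/mm³ (equivalently cells/µL). This changes one unit in two places and costs nothing.

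Reconcile Table 3 and the screening column of Appendix 1a (with footnote s) with Sections 4.1.2 and 4.6.1, so that a creatinine result is available and the clearance reviewed before randomization. Naming creatinine as a screening assessment would bring it under the existing allowance in Section 4.6.4, so a routine result from the same admission would suffice. For most hospitalized patients this should need no extra sample. At most it moves one local laboratory value from Day 1 to screening.

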4.2 METHOD OF TREATMENT ASSIGNMENT AND BLINDING

The randomization of patients will be managed by a central Interactive Voice and Web Response System (IxRS) through use of a dynamic hierarchical algorithm which includes a random component. The treatment assignments will be unblinded to selected Sponsor personnel to facilitate ongoing monitoring of safety and tolerability, including members of the IMC and SOC.

All patients will be randomly assigned to receive 3600 mg MHAA4549A, 8400 mg MHAA4549A, or placebo at a 1:1:1 ratio stratified by country, whether patient is on PPV versus supplemental O₂ at randomization, and whether the patient has suspected or

confirmed bacterial pneumonia vs no bacterial pneumonia at randomization. Initially GV29216 randomly assigned patients to receive either 3600 mg MHAA4549A, or placebo at a 1:1 ratio. The updated randomization scheme takes into account the numbers already allocated to these two arms and strata prior to allocating to the three arm design so that by the end of the study there will be an approximate 1:1:1 allocation between the three arms.

All patients will receive oseltamivir (as described in [Table 2](#)) for a minimum of 5 days. Treatment for longer than 5 days is permitted based on local investigator discretion.

Unblinded personnel (i.e., unblinded site pharmacist or other designated, qualified unblinded study personnel) at each study site will prepare the IV infusions of study drug, as described in [Section 4.3.3](#). The Sponsor will provide masking bags and blinded study personnel will administer the study drug. The other parties who are involved in the conduct of the study (i.e., patients and blinded site personnel) will remain blinded to patient-specific treatment assignments until the final database lock after the completion of the study.

Bioanalytical laboratory personnel responsible for performing PK assays will be unblinded to patients' treatment assignments to identify appropriate PK samples to be analyzed. Samples from patients assigned to the comparator arm will not be analyzed except by request (e.g., to evaluate a possible error in study drug administration).

While PK samples must be collected from patients assigned to the comparator arm to maintain the blinding of treatment assignment, PK assay results for these patients are generally not needed for the safe conduct or proper interpretation of this trial.

If unblinding is necessary for patient management (e.g., in the case of an SAE for which patient management might be affected by knowledge of treatment assignment), the investigator will be able to break the treatment code in IxRS. Treatment codes should not be broken except in emergency situations. If the investigator wishes to know the identity of the study drug for any other reason, they should contact the Medical Monitor directly. The investigator should document and provide an explanation for any premature unblinding (e.g., accidental unblinding, unblinding due to an SAE).

For regulatory reporting purposes, and if required by local health authorities, the Sponsor will break the treatment code for all suspected unexpected serious adverse reactions (SUSAR) (see [Section 5.4](#)) that are considered by the investigator or Sponsor to be related to study drug.

4.3 STUDY TREATMENT

4.3.1 Formulation, Packaging, and Handling

4.3.1.1 MHAA4549A and Placebo

MHAA4549A will be supplied by the Sponsor in a sterile, preservative-free liquid solution in a single-use 15-mL USP/Ph. Eur. Type 1 glass vials filled to deliver 10 mL (500 mg) of MHAA4549A solution.

MHAA4549A placebo will be provided as a clear, colorless, sterile, preservative-free liquid solution and has the same vial configuration as the drug product.

For information on the formulation and handling of MHAA4549A, see the *pharmacy manual* and the *Investigator's Brochure*.

4.3.1.2 Oseltamivir (Tamiflu®)

Oseltamivir (Tamiflu®) is an influenza NAI indicated for treatment of acute, uncomplicated influenza. The Sponsor will provide 75-mg capsules of oseltamivir for up to a 10-day treatment course (for 75- or 150-mg BID regimens). For renal dose adjustments, follow local standard-of-care practice/local package insert and document in the eCRF. Capsules other than 75 mg (for 75- or 150-mg BID regimens) cannot be provided through the study IxRS. In these instances, the study site may supply the appropriate dose and be reimbursed by the Sponsor.

For information on the formulation, packaging, and handling of oseltamivir; see the local prescribing information for oseltamivir.

Storage: Capsules should be stored at 25°C (77.7°F); excursions are permitted to 15°C to 30°C (59°F to 86°F).

4.3.2 Dosage, Administration, and Compliance

4.3.2.1 MHAA4549A and Placebo

Administration of MHAA4549A or placebo will be performed in a setting with emergency medical equipment and personnel who are trained to monitor for and respond to medical emergencies. A qualified physician or medically qualified designee will be on site during study drug administration for all patients.

A single dose of MHAA4549A or placebo will be delivered by IV infusion following dilution in 0.9% normal saline over approximately 120 minutes. Study drug should be delivered using a 0.20- to 0.22- μ m in-line filter. Compatibility testing has shown that MHAA4549A is stable when diluted in 0.9% normal saline in a polyvinylchloride bag, polyolefin bag, or ethylene vinyl acetate bag (EVA), at concentrations of 0.24 mg/mL up to 27.0 mg/mL. Study drug must be administered within the treatment window outlined in [Section 3.1.1](#). Further detailed instructions for preparation of study drug can be found in the Pharmacy Manual.

Subjects who experience a moderate-to-severe infusion-related reaction should have their infusion stopped. The infusion should not be restarted. The infusion will be discontinued in the event that the subject experiences a serious reaction and further dosing of subjects will be halted until the safety of the drug is assessed.

There are no recommended dosage modifications for MHAA4549A since it is a single infusion. Any overdose or incorrect administration of study drug should be noted on the Study Drug Administration electronic Case Report Form (eCRF). AEs associated with an overdose or incorrect administration of study drug should be recorded on the Adverse Event eCRF. General supportive measures will be taken to manage any AEs associated with overdose. Patients experiencing such AEs will be followed up clinically until the event has resolved.

Trained clinical site staff responsible for adequate and accurate study drug administration, accounting, and management will administer study drugs to patients. Study drug preparation and dosing instructions will be provided to each site. The exact times of study drug administration will be recorded in the relevant dispensing/administration logs and patient's source notes. Any noncompliance or problems with study drug administration will be recorded in the patient's source notes and reported to the Sponsor if appropriate.

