4.3.3 Investigational Medicinal Product Accountability

Investigational medicinal products (IMPs) required for completion of this study (i.e., MHAA4549A and 75-mg oseltamivir capsules) will be provided by the Sponsor. The

study site will acknowledge receipt of IMPs and confirm the shipment condition and content. Any damaged shipments will be replaced.

The IMP will be stored in a secure pharmacy or locked area with access limited to authorized personnel, in accordance with the details provided in the Investigator's Brochure and Pharmacy Manual. Upon receipt, MHAA4549A and placebo vials must be refrigerated at 2°C to 8°C until use. MHAA4549A does not contain antimicrobial preservatives; therefore, care must be taken to ensure that the solution for infusion is not microbiologically compromised during preparation. Dilute under appropriate aseptic conditions using 0.9% normal saline. The solution for infusion should be used immediately. If not used immediately, in-use storage times and conditions prior to use should not exceed 24 hours at 2°C to 8°C and/or 4 hours at ambient temperature (18°C–24°C). If the dose solution is stored at 2°C–8°C, it should be removed from refrigeration and allowed to reach room temperature prior to administration. If the infusion is interrupted and the combined ambient temperature storage and interruption time exceeds 4 hours, prepare a new dose solution to resume the infusion (see the Pharmacy Manual). Protect dose solutions from heat and intense light.

The total duration from the preparation of dose solutions to the end of infusion should not exceed 24 hours. Vials are intended for single use only; therefore, any remaining solution should be discarded (see the Pharmacy Manual).

IMPs will either be disposed of at the study site according to the study site's institutional standard operating procedure or returned to the Sponsor or their delegate with the appropriate documentation. The site's method of IMP destruction must be agreed to by the Sponsor. The site must obtain written authorization from the Sponsor before any IMP is destroyed, and IMP destruction must be documented on the appropriate form.

Accurate records of all IMPs received at, dispensed from, returned to, and disposed of by the study site should be recorded on the Drug Inventory Log.

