4.9.2 Study Treatment Discontinuation

Patients must discontinue MHAA4549A infusion and therefore treatment if they experience any of the following:

- Life threatening infusion-related reactions

Patients must discontinue oseltamivir treatment if they experience any of the following:

- Pregnancy
- Serious skin/hypersensitivity reactions

The primary reason for study treatment discontinuation should be documented on the appropriate eCRF.

The IMC and SOC may recommend to permanently discontinue dosing for all patients within one or both study arms in the event of a general safety concern.

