Appendix 9 (cont'd)

DAIDS Toxicity Grading Tables for Laboratory Abnormalities

From the FDA Guidance document 'Toxicity Grading Scale from Healthy Adult and Adolescent Volunteers Enrolled in Preventative Vaccine Clinical Trials'

ENZYMES				
	Grade 1	Grade 2	Grade 3	Grade 4
AST (SGOT)	1.1 - <2.0×ULN	2.0 - <3.0×ULN	3.0 – 8.0×ULN	>8.0×ULN
ALT (SGPT)	1.1 - <2.0×ULN	2.0 - <3.0×ULN	3.0 – 8.0×ULN	>8.0×ULN
GGT	1.1 - <2.0×ULN	2.0 - <3.0×ULN	3.0 – 8.0×ULN	>8.0×ULN
Alkaline Phosphatase	1.1 - <2.0×ULN	2.0 - <3.0×ULN	3.0 – 8.0×ULN	>8.0×ULN
Amylase	1.1 – 1.5×ULN	1.6 – 2.0×ULN	2.1 – 5.0×ULN	>5.1×ULN
Lipase	1.1 – 1.5×ULN	1.6 – 2.0×ULN	2.1 – 5.0×ULN	>5.1×ULN
*CPK – mg/dL	1.25 – 1.5×ULN	1.6 – 3.0×ULN	3.1 – 10.0×ULN	>10×ULN

* From the FDA Guidance document 'Toxicity Grading Scale from Healthy Adult and Adolescent Volunteers Enrolled in Preventative Vaccine Clinical Trials'

URINALYSIS				
	Grade 1	Grade 2	Grade 3	Grade 4
Proteinuria	1+ or 200 mg – 1 g loss/day	2-3+ or 1-2 g loss/day	4+ or 2-3.5 g loss/day	Nephrotic syndrome or >3.5 g loss/day
Hematuria	Microscopic only <10 RBC/hpf	Gross, no clots >10 RBC/hpf	Gross, with or without clots, OR red blood casts	Obstructive or required transfusion
*Glucose	Trace	1+	2+	Hospitalization for hyperglycemia

From the FDA Guidance document 'Toxicity Grading Scale from Healthy Adult and Adolescent Volunteers Enrolled in Preventative Vaccine Clinical Trials'

Appendix 10

Anaphylaxis Precautions and Management

Administration of MHAA4549A will be performed in a setting with emergency medical equipment and personnel who are trained to monitor for and respond to medical emergencies. A qualified physician *or medically qualified designee* will be on site during study drug administration for all patients.

The following equipment is needed in the event of a suspected anaphylactic reaction during study drug infusion:

- Airway management equipment
- O₂
- Epinephrine for subcutaneous, intravenous, and/or endotracheal use in accordance with standard practice
- Antihistamines
- Corticosteroids
- IV infusion solutions, tubing, catheters, and tape

The following are the procedures to follow in the event of a suspected anaphylactic reaction during study drug infusion:

- Stop the study drug infusion.
- Maintain an adequate airway.
- Administer antihistamines, epinephrine, or other medications as required by patient status and directed by the physician in charge.
- Continue to observe the patient and document observations.

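### Sections 4.3.2.1 and 4.9.2 set different, unreconciled thresholds for ending the infusion after an infusion-related reaction

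*Combined protocol and SAP*

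**What the plan says.** All references are to the Version 7 protocol text.

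- **Section 4.3.2.1** (dosing and administration) gives a rule for the patient: "Subjects who experience a moderate-to-severe infusion-related reaction should have their infusion stopped. The infusion should not be restarted". It follows with a rule that reaches beyond the patient: "The infusion will be discontinued in the event that the subject experiences a serious reaction and further dosing of subjects will be halted", the halt lasting until the drug's safety has been assessed.
- **Section 4.9.2** (study treatment discontinuation) opens its list with "Patients must discontinue MHAA4549A infusion and therefore treatment if they experience any of the following". The list has one entry: "Life threatening infusion-related reactions". On wider action it says: "The IMC and SOC may recommend to permanently discontinue dosing for all patients within one or both study arms", where there is a general safety concern.
- **Section 4.3.3** (product accountability) covers an interrupted infusion. If the "combined ambient temperature storage and interruption time exceeds 4 hours, prepare a new dose solution to resume the infusion". It names no cause of interruption.
- **Appendix 10** (anaphylaxis) instructs staff, for a suspected anaphylactic reaction, "Stop the study drug infusion". It does not address restarting.

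**The concern.** Two sections that a site would consult on the same question give different triggers, and neither points to the other. Section 4.9.2 carries the title that staff would look for, and Section 4.6.11 treats it as the reference for decisions on discontinuation. Someone checking it during a 120-minute infusion would not find the rule in 4.3.2.1.

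Two things are at stake. The first is the patient: whether an investigational infusion is ended should not depend on which page is open. The second is the data. Section 6.2 tabulates early treatment discontinuations, their reasons and protocol deviations by arm, and Section 6.5 makes discontinuation due to adverse events a safety parameter. If sites apply different thresholds, the same reaction is counted differently from site to site and the dose received varies with it, in a trial comparing two doses with placebo.

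The halt sentence raises a related question. It states an outcome for all further dosing but no decision-maker.

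**Working it through.** No arithmetic underlies the finding itself; it is a comparison of text. Table 5 in Section 5.3.3 grades severity as mild (1), moderate (2), severe (3) and potentially life-threatening (4). Neither 4.3.2.1 nor 4.9.2 cites that table, so mapping their terms to its grades is an assumption.

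| Reaction | Section 4.3.2.1 | Section 4.9.2 | Result |
|---|---|---|---|
| Mild, not serious | No stopping rule | Not listed | Both silent |
| Moderate or severe, not life-threatening | Stop, no restart | Not listed | Thresholds differ |
| Life-threatening | Discontinue (a life-threatening event is serious under Section 5.2.2) | Mandatory discontinuation | Agree for the patient |

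The mismatch is confined to the middle row.

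**Section 4.3.3.** Its sentence concerns how long a diluted solution may be kept. It sets no severity threshold and does not mention reactions. It would collide with the no-restart instruction only if read as permission to resume after a moderate-to-severe reaction, which it does not say. What is missing is a statement of whether its resumption text applies after a reaction.

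**The halt.** Under 4.3.2.1 a serious reaction leads to a halt, stated as something that will happen. Under 4.9.2 the committees may recommend permanent discontinuation of dosing, and under 3.1.1 they may recommend stopping enrolment. Section 4.3.2.1 does not say who orders the halt, who assesses safety or who lifts it, and it does not point to the committees. Section 5.2.2 also warns that severe and serious are different concepts, so 4.3.2.1 moves from a severity scale to a seriousness criterion without saying how they relate.

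**How often it could arise.** The documents give no rate for severely ill patients. Section 1.3.2 reports that the drug has not been associated with infusion-related reactions. Section 1.2.2 counts 84 dosed healthy volunteers, of whom 8 received 8400 mg or 10800 mg (Section 1.2.2.2). Assuming that report means zero events, the one-sided 95% upper bound is 1 − 0.05^(1/n):

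- n = 84: 1 − 0.05^(1/84) ≈ 3.5%
- n = 8: 1 − 0.05^(1/8) ≈ 31%

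These bounds concern any associated reaction in healthy volunteers. They do not estimate the rate here; they show only that earlier experience, especially at the higher doses, does not establish that the case is negligible.

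**The case against.** The strongest reply is that the two sections can be read together. Section 4.9.2 states when discontinuation is compulsory and nowhere tells a site to continue or resume. Section 4.3.2.1 uses the weaker verb for lesser reactions. On that reading there are two tiers, and a site that follows 4.3.2.1 satisfies both. This stands in part: a reader might infer that sites can comply fully while treating the same reaction in opposite ways, and the documents do not support that. A site that continues after a moderate reaction departs from 4.3.2.1. But nothing in either section says that tiers are intended. The Version 7 summary of changes shows the 4.3.2.1 paragraph being added while 4.9.2 keeps its Version 5 wording, which is consistent with an incomplete edit. That history explains the origin only; the mismatch lies in the current text.

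A reader might also count Section 4.3.3 as a third conflicting rule. It is not: it is a solution-stability instruction, and the only gap is a cross-reference. Appendix 10 agrees with stopping.

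On the halt, a temporary pause, a permanent end to dosing and a stop to enrolment are different actions and do not strictly contradict one another. Section 3.1.2 places committee procedures in a separate agreement that may name the decision-maker. This too stands in part: the gap is that 4.3.2.1 neither names one nor points to that agreement.

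Finally, blinded staff give the infusions using masking bags (Section 4.2), and efficacy is analysed by randomised arm (Section 6). Different site readings would therefore not in themselves favour one arm. This is accepted.

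**Conclusion.** The inconsistency is real and narrow. Sections 4.3.2.1 and 4.9.2 state different thresholds for ending the infusion, and the difference covers reactions that are moderate or severe but not life-threatening. A site relying on 4.9.2 could continue an infusion that 4.3.2.1 says to stop without restart. The halt in 4.3.2.1 has no named decision-maker and is not connected to the IMC and SOC recommendation described in 4.9.2.

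The consequences are inconsistent patient handling and inconsistent counts of discontinuations and deviations. Bias between arms is something a reader might infer, but the documents give no basis for it. The number of patients affected cannot be stated, because no reaction rate is given for this population. The conclusion assumes that the severity terms carry their Table 5 meaning and that the separate IMC and SOC agreement, which is not among the documents, does not change the site-level rule. It takes no position on which threshold is right.

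**What to change.** 1. The sponsor reconciles 4.3.2.1 and 4.9.2 into one consistent rule of its own choosing, covering the severity threshold and whether an infusion may be restarted, with each section referring to the other. If tiers are intended, the text should say so.
2. Section 4.3.3 and Appendix 10 cross-reference that rule, and 4.3.3 states whether its resumption text applies after a reaction.
3. The halt sentence in 4.3.2.1 is linked to the IMC and SOC process, stating who orders the halt, who assesses safety and who lifts it, or pointing to the agreement where this is set out.
4. Optionally, record the volume given at each stopped infusion. The primary reason for discontinuation is already captured (Section 4.9.2) and reasons are summarised by arm (Section 6.2), so volume is the only addition.

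The cost is a protocol clarification or minor amendment. Sample size, randomisation and planned analyses are unaffected.
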